2.5 Rationale

Preclinical and early Phase 0 data demonstrated that IPdR was well tolerated and effective as a radiosensitizer. These data provide justification for further clinical evaluation since there are no clinical data of IPdR and WBRT.

BMs are the most common intracranial malignancy, and a cause of significant neurologic morbidity and mortality. While there is a higher likelihood for development of BMs based on tumor type, any malignancy may metastasize to the brain. Therefore, all tumor types will be evaluated with the exception of traditionally radiosensitive tumors (germ cell, lymphoma, leukemia).

The starting dose for po IPdR for Phase 1 testing is based on the most sensitive (lower MTD) of the two animal species tested, *i.e.* ferrets and rats.[44, 45] The MTD for po IPdR in ferrets, the most sensitive species, was determined to be $\leq 150 \text{ mg/kg/d} \times 14 \text{ days}$ [45], which is equivalent to $850 \text{ mg/M}^2/\text{day} \times 14 \text{ days}$. The human equivalent dose (HED) is also $850 \text{ mg/M}^2/\text{day}$, the same as the ferret dose, based on body surface area (BSA).[48] Based on these calculations and pre-clinical animal data, $1/10^{\text{th}}$ of the MTD is $85 \text{ mg/M}^2/\text{day}$ ($\approx 150 \text{ mg}$), the proposed starting dose for our proposed Phase 1 trial.

This Phase 1 study will determine the maximum tolerated dose of single agent IPdR when given in conjunction with WBRT for palliation in patients with brain metastases. Once the MTD of single agent IPdR and WBRT is determined, future studies will evaluate the efficacy of IPdR and WBRT in controlling intracranial metastatic disease.

2.5.1 Rationale for study modification (Amendment #06 including revised submissions)

Multiple amendments were requested in the study protocol to boost accrual. These are detailed below:

- a. Change in two part dose-escalation design: Based on the published results from the study 8866 (phase-0) and updated results from the NCI 9882/ NCT02381561 noted in sections above along with recommendations from the CTEP medical officer, it was elected to stop accrual to part 1 at dose-level 1B (300 mg) and directly activate part 2 of the study at 1200 mg dosing.

At the time of submission of amendment #6 (Dt 12/12/2017), #6 rev (02/26/2018) and the current version, one patient each was accrued at dose levels of 150 and 300 mg with no DLT.

Based on the recommendations noted in the amendment #6rev disapproval letter, the study accrual will be suspended at dose level 1B with the plan to open the study directly at 1200 mg dose level of part 2, once the amendment has been approved.

- b. Change in dose-escalation schedule: The dose-escalation schedule was also amended. The original modified accelerated design was found to restrict speed of accrual, since once a patient was registered, for the duration of pre-study work-up, study treatment and post-study DLT assessment, no other patient could be accrued on the study. This lead to non-availability of slots for any other eligible patient and was felt to be a barrier in accrual. Hence, per the communication received from the CTEP medical officer, a change to a 3+3 design was recommended.

A conservative 3+3 phase-1 study design poses unique challenges for the brain metastases population to be treated with WBRT + study drug related to high baseline incidence of adverse events in this population and due to inherent limitations of a conservative 3+3 design. The most recent large-scale multi-institutional randomized trial of post-operative SRS to the surgical cavity versus WBRT (NCCTG N107C/CEC.3, Brown et al., Lancet Oncol 2017), showed grade 3 or worse adverse events (irrespective of attribution) in 36 (39%) patients in the SRS group and 37 (40%) patients in the WBRT group. Corresponding grade 3 or more events that were possibly related to treatment were 11 (12%) patients in the SRS group compared with 17 (18%) patients in the WBRT group. Despite, 77% of patients having only one lesion which was surgical resected and an ECOG PS of 1 or less in 90% patients, only about 50% patients survived one year in both the arms. In patients with 1-3 brain metastases (SRS alone candidates), another multi-institutional randomized trial of SRS alone or SRS + WBRT (NCCTG N0574 study, Brown et al, JAMA 2016), at least one grade 3 or more AE was seen in 41.4-43.1% of patients. Median overall survival

was only 10.4 months in SRS alone and 7.4 months in SRS + WBRT patients. The rates of adverse events are expected to be higher and survival outcomes lower in non-surgical patients with multiple brain metastases, which form the patient population in this study. Indeed, in the phase 3 randomized trial of WBRT plus motexafin gadolinium for patients with brain metastases from non-small cell lung cancer (Mehta et al, Int J Radiat Oncol Biol Phys 2009) or with WBRT + efaproxiral for breast cancer (Suh et al., J Clin Oncol 2006), the incidence of \geq Grade 3 toxicity with WBRT alone was approximately 10%, while with WBRT + drug combination was approximately 25-30%.

As such, in the setting of poor overall prognosis, high baseline incidence of adverse events (related to the presence of brain metastases or WBRT) and since the study design is changed to a more conservative 3+3 design which may be at risk of falsely under-predicting MTD due to random occurrence of an AE at a lower dose level, it is justified to explore treatments with higher incidence of adverse events if it can help improve the dismal survival outcomes.

2.6 Correlative Studies Background

As the %IUDR-DNA cellular incorporation in human tumor xenografts in athymic mice was linearly related to the IPdR dose when given po qd x 6-14 days [39, 41, 47], we will correlate %IUDR-DNA cellular incorporation in human tumor biopsies as an exploratory biomarker of tumor radiosensitization in a cohort of 6 brain metastases cancer patients receiving the RP2D by linear regression. [name], Associate Director for Developmental Therapeutics, DCTP, NCI will actively participate in the PK and %IUDR-DNA cellular incorporation analyses.

2.6.1 Pharmacokinetics of IPdR

The clinical pharmacology of PO IPdR was characterized in the initial, DCTD-sponsored phase 1 trial 8866. Patients received a single PO dose of IPdR.[46] Plasma concentrations of the active metabolite IUDR generally increased with increasing dose. At dose level (DL) 5 (2400 mg IPdR), plasma IUDR levels reached a peak of 4.0 ± 1.02 mcM after 1.67 ± 1.21 hours, remained above 1 mcM for 3 to 4 hours, and declined with a half-life of 1.5 hours. Plasma exposure values of the major secondary metabolite IU increased more than proportionally as doses were doubled, and remained at a sustained high level (near 100 mcM) for 10 hours in four of the 6 patients treated at DL 5, indicating disproportionate accumulation due to saturation of metabolic elimination. IPdR and its metabolites, IUDR, IP, and IU, were detectable in urine samples from patients receiving 2400 mg of IPdR. Twelve percent ($\pm 8\%$) of the dose was recovered over 24 hours; of the metabolites measured in urine, $90 \pm 13\%$ consisted of IU. Previous clinical trials had defined 1 mcM as the minimum IUDR plasma concentration for efficacy[31, 49]; since DL 5 of this trial had achieved a mean peak IUDR plasma concentration of around 4 mcM, investigators concluded that PO IPdR may prove to show clinical antitumor activity, and future trials may focus on determining the optimal dosing schedule in sequence with RT.

2.6.2 %IUDR-DNA Incorporation into Tumor

Athymic nude mice bearing HCT-116 human colon cancer xenografts, either as liver metastases, subcutaneous (SC) flank tumors, or both, were administered IPdR PO for 6 days at its RP2D (1 g/kg/day).[39] This treatment resulted in a 2-to 3-fold greater incorporation of IUDR into tumor DNA than IUDR administered at its RP2D (250 mg/kg/day), indicating a greater potential for radiosensitization.

In a second study, athymic mice with HT29 human colon cancer xenografts were treated up to 2 g/kg PO IPdR for 6 days and the investigators found < 1.5 times increase in the percentage of IUDR-DNA in the tumor xenografts.[40] A subset of the mice with SC xenografts measuring 0.25-0.3 cm² were treated with RT (2 Gray [Gy]/day for 4 days) with or without PO doses of IPdR at the RP2D of 1000 mg/kg/day for 6 days. A tumor

regrowth assay demonstrated a 1.5-fold improvement in outcome (time to regrowth of tumor to 300% of pre-treatment volume) of the IPdR + RT group versus RT alone. Mice with U251 human glioblastoma xenografts were treated with 750 or 1500 mg/kg/day IPdR over 14 days.[41] A significant sensitizer enhancement ratio (SER), calculated as the ratio of growth delay [time to 300% original tumor volume] after agent + RT to the delay after RT alone) was found for PO IPdR + RT (SER=1.31, P=0.05) but not for 14-day CIV IUdR + RT (SER=1.07, P=0.57), indicating that IPdR could be a useful clinical radiosensitizing agent.

Deficiencies in the mismatch repair (MMR) system have been implicated in the genesis of hereditary nonpolyposis colon cancer and an increasing number of sporadic cancers (Peltomaki, 2003). Athymic nude mice with an isogenic pair of human colon cancer xenografts HCT116 (MMR⁻, hMLH1⁻) and HCT116/3-6 (MMR⁺, hMLH1⁺), were treated with PO IPdR (1g/kg/d) every day for 14 days.[47] On Days 11 to 14, RT was delivered to the tumor xenografts with 2 Gy or 4 Gy per fraction for 4 days. The tumor size and the body weight were monitored daily until the tumors grew to \leq 300% of their pre-irradiation volume. The tumor volumes were estimated by the formula: $R1 \times R2 \times R2/2$, where $R1$ is the maximum diameter and $R2$ is the rectangular diameter. Tumor regrowth delay was calculated as the area between the 300% volume line and the growth curves for the various control and treatment groups. Substantial increases in regrowth delay were found in both HCT116 and HCT116/3-6 tumor xenografts and there was substantial radiosensitization in both HCT116 and HCT116/3-6 tumor xenografts.

Athymic nude mice with human glioblastoma (U251) SC xenografts were treated with IPdR: 1) 500 mg/kg of every other day (QOD); 2) 500 mg/kg QD; 3) 166 mg/kg three times a day (TID); or 4) vehicle alone (control).[43] On the IPdR treatment Days 11 to 14 (for the QD, TID, and control groups) and Days 25 to 29 (for the QOD group), RT was delivered using 2 Gy/fraction for 4 days to the tumor xenografts. The tumor regrowth assay showed in all three IPdR treatment groups enhanced tumor growth delay compared to control (QOD, 29.4 days; QD, 29.7 days; TID, 34.7 days; radiotherapy alone 15.7 days). The SER of each schedule was calculated: QOD 2.17; QD, 2.20; and TID, 2.56. The QOD schedule also resulted in reduced systemic toxicity.

In the most recent study in mice, athymic male nude mice (6–8 weeks old) were implanted with SC U87 xenograft tumors (4×10^6 cells) and then randomized to 10 treatment groups receiving increasing doses of PO IPdR (0, 100, 250, 500, and 1000 mg/kg/d) administered QD for 14 days with or without RT (0 or 2 Gy/d for 4 d) on Days 11–14 of IPdR treatment.[42] At Day 31, the mean tumor volume reduced from $1609 \pm 285 \text{ mm}^3$ to $821 \pm 113 \text{ mm}^3$ with RT alone. IPdR treatment with or without RT caused a dose-dependent reduction in tumor volume: 250 mg/kg/d for 14 days (IPdR alone, $1040 \pm 105 \text{ mm}^3$; IPdR + RT, $551 \pm 86 \text{ mm}^3$); 500 mg/kg/d for 14 days (IPdR alone, $960 \pm 131 \text{ mm}^3$; IPdR + RT, $268 \pm 69 \text{ mm}^3$); 1000 mg/kg/d for 14 days (IPdR alone, $718 \pm 99 \text{ mm}^3$; IPdR + RT, $309 \pm 60 \text{ mm}^3$). The SER was approximately 2–3 for the two lower IPdR dose groups and 5–6 for the two higher IPdR dose groups. These results indicated that the efficacy of PO IPdR plateaus around $\geq 500 \text{ mg/kg/day}$.

Correlation of tumor response using RECIST Criteria with the %IUDR-DNA cellular incorporation in tumor from biopsies of tumors in patients with brain metastases at the RP2D will be analyzed to determine the tumor response relationship to the %IUDR-DNA cellular incorporation in tumor on Day 8 of the 28-day IPdR treatment based on HPLC and flow cytometry measurements. A tumor biopsy on Day 8 of IPdR treatment was selected to provide for measurable IUDR-DNA incorporation in tumor and to eliminate the effect of RT on tumor tissue as the tumor biopsy will be performed prior to the initiation of RT. Tumor biopsy is not required for participation in this study. Tumor biopsy should only be considered for tumors that are easily accessible and would not subject that patient to a high risk of morbidity as a result of a tumor biopsy. Otherwise, if tumor is easily accessible and biopsy would pose minimal risk to the patient, then tumor biopsy should be performed. A biopsy may be taken of the primary tumor or any extracranial metastasis. A biopsy of the brain metastasis is not permitted. In this analysis, tumor response is the dependent variable and can be binomial (i.e. response vs. no response) or multinomial (i.e. complete response, partial response, stable disease or progressive disease) and the %IUDR-DNA cellular incorporation is the independent variable.

The survival times will also be obtained from the brain metastases cancer patients and, if data allow, will be analyzed using a Cox proportional hazards model with %IUDR-DNA cellular incorporation in tumor as the covariate. However, given the variable tumor types and extent of disease, according to the eligibility criteria, a valid survival analysis is unlikely.

2.6.3 %IUDR-DNA Incorporation into Normal tissues

In the pre-clinical *in vivo* testing of po IPdR as a prodrug for IUDR-mediated radiosensitization, ≥ 2 -fold decreases in %IUDR-DNA incorporation in proliferating dose-limiting normal tissues (bone marrow and intestine) following PO IPdR were consistently found compared to PO or CIV infusions of IUDR (using RP2D schedules) in 4 different human tumor xenografts in athymic mice.[39-42] In prior clinical Phase 1 trials of CIV infusions of IUDR (\pm biochemical modulators), the %IUDR-DNA incorporation in circulating granulocytes during and following the IUDR infusion as a surrogate for a proliferating normal human tissue (bone marrow) has been measured.[32, 50-54] In general, the %IUDR-DNA incorporation in circulating granulocytes increased linearly with a linear increase in steady-state plasma levels of IUDR. Additionally, high ($\geq 6\%$) %IUDR-DNA levels in peripheral granulocytes predicted for systemic bone marrow toxicity to CIV IUDR. In the pre-clinical studies of po IPdR daily for 14 days in athymic mice and ferrets,[39, 41, 47] the %IUDR-DNA incorporation was $\leq 2\%$ in circulating granulocytes following treatment and no changes in blood counts were found in ferrets and rats,[44, 45] suggesting that bone marrow toxicity may not be dose-limiting for PO IPdR in humans. Additionally, no myelosuppression or bone marrow abnormalities were seen in the IPdR toxicology studies, where IPdR was given once daily for 14 days in ferrets and for 28 days in rats.[44, 45]

Correlation will be performed of the %IUdR-DNA cellular incorporation in peripheral (circulating) granulocytes as an exploratory biomarker of bone marrow acute normal tissue toxicity with the po IPdR RP2D and RP2D pharmacokinetics. This exploratory assay was originally developed in [name] laboratory at NCI.[55] Additionally, we do not expect a linear relationship between the %IUdR-DNA cellular incorporation in circulating granulocytes and peripheral blood counts measured weekly during RP2D drug exposures and at Day 29 and Week 8 follow-up. Nevertheless, we will test the hypothesis that IPdR drug dose and drug plasma pharmacokinetics will be linearly related to the %IUdR-DNA cellular incorporation in circulating granulocytes.

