1.3 Correlative Objectives (in 6 additional patients accrued at RP2D)

1.3.1 To assess for biochemical evidence of IPdR effect in normal tissues (circulating granulocytes) by measuring %IUDR-DNA cellular incorporation by flow cytometry and high-pressure liquid chromatography (HPLC) analyses as an exploratory biomarker for the following effects:

- The %IUDR-DNA tumor cell incorporation from Day 8 extracranial tumor biopsies in brain metastasis cancer patients receiving RP2D doses of IPdR as an exploratory biomarker of tumor radiosensitization using RECIST criteria.
- The %IUDR-DNA cellular incorporation in patients' circulating granulocytes taken weekly during the 28-day IPdR RP2D dose, on Day 29, and Week 8 as an exploratory biomarker of IPdR systemic toxicities to bone marrow as measured by serial CBC/differential values

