11. MEASUREMENT OF EFFECT

Although the clinical benefit of IPdR has not yet been established, the intent of offering this treatment is to provide a possible therapeutic benefit, and thus the patients in part 2 of the study (to exclude patients treated at lower doses in part 1 thereby minimizing heterogeneity in response) will be carefully monitored for tumor response in addition to safety and tolerability. Patients with measurable disease will be assessed by standard criteria noted below. Each eligible patient must have at least one measurable lesion that will be included in the radiation treatment volume. If the measurable disease is restricted to a solitary lesion, the presence of malignancy must be confirmed by cytology/histology. Tumor lesion(s) included within the high dose radiation treatment volume ($\geq 95\%$ isodose line) will be considered as the target lesions for response evaluation. Patients with measurable disease will be assessed by standard criteria. For the purposes of this study, patients should be evaluated at baseline at 6 months (± 2 weeks) from the completion of WBRT. As guided by institutional practices, MRIs are also recommended during follow-up visits every 2 months (± 1 week) for the first 6 months and every 3-4 months (± 2 weeks) for the next 6 months from the completion of WBRT.

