13.4.3 Biomarkers

Biomarker data will be explored in a simple descriptive manner as data are limited in this small phase 1 study.

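### Tumour %IUdR-DNA is measured in an extracranial lesion and RECIST response in brain lesions, so regressing one on the other cannot support a radiosensitization biomarker without an assumption that the plan neither states nor tests

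*Combined protocol and SAP*

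**What the plan says.** Objective 1.3.1 concerns "tumor cell incorporation from Day 8 extracranial tumor biopsies in brain metastasis cancer patients receiving RP2D doses of IPdR", to be used "as an exploratory biomarker of tumor radiosensitization using RECIST criteria". Section 2.6 names linear regression in a cohort of six patients. Section 2.6.2 sets out the analysis: "Correlation of tumor response using RECIST Criteria with the %IUDR-DNA cellular incorporation in tumor from biopsies of tumors in patients with brain metastases". It adds: "In this analysis, tumor response is the dependent variable and can be binomial" or multinomial, with incorporation as the independent variable. The same section allows a Cox model of survival on tumour incorporation if the data permit, and then says that a valid survival analysis is unlikely.

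On the biopsy site, section 2.6.2 says "A biopsy may be taken of the primary tumor or any extracranial metastasis" and "A biopsy of the brain metastasis is not permitted". Section 9.2.2 repeats both rules. On response, section 11 says that lesions inside the high-dose radiation volume "will be considered as the target lesions for response evaluation". Section 11.1 is headed for intracranial metastases, and brain MRI is the only tumour imaging in the study calendar.

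The statistical section is more modest. Section 13.4.3 says: "Biomarker data will be explored in a simple descriptive manner as data are limited in this small phase 1 study". The synopsis version of the correlative objective speaks only of evaluating incorporation in accessible tumour outside the brain, and mentions neither RECIST nor radiosensitization.

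**The concern.** The predictor and the outcome come from different lesions. The biopsied lesion normally receives no study radiation and is not followed for response. The brain lesions are irradiated and followed, but their incorporation is unknown. A correlation, or the lack of one, could be reported as evidence for or against radiosensitization although lesion, radiation dose and possibly drug delivery all differ between the two sides of the regression.

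Separately, the objectives and background describe regression, categorical-response and Cox models, while the statistical section and synopsis describe a summary only. Whoever writes the report could follow either.

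**Working it through.** The documents give no alpha, power, effect size or precision for this correlation, so there is no planned figure to reproduce. The main check sets the sections side by side.

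| Element | Biopsied lesion | Lesions assessed for response |
|---|---|---|
| Location | Primary or extracranial metastasis (2.6.2, 9.2.2) | Intracranial (11.1) |
| Study radiation | Normally none; WBRT targets the cranial contents (5.1.4.3) | Yes; inside the high-dose volume (11) |
| %IUdR-DNA | Day 8 (9.2.2) | Never; biopsy not permitted |
| RECIST response | None planned | Brain MRI, required at 6 months after WBRT (5.5, calendar) |

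The protocol's own rationale is a same-tissue one. Section 9.2.1 relates incorporation in a cell or tissue to radiosensitization of that cell or tissue. In the radiosensitization xenograft studies in 2.6.2, the irradiated tumour is the one whose regrowth or volume was measured. No section reports, or plans to collect, data linking extracranial to brain-metastasis incorporation.

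The arithmetic below shows how little the regression could deliver. Two-sided 0.05 and all correlations are assumptions for illustration.

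1. **Largest case, n = 6, Pearson correlation.** Critical |r| = t / √(n − 2 + t²), with t = 2.776 on 4 df. This gives 2.776 / √(4 + 7.706) = 0.811.

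2. **Dilution by the surrogate.** Let ρ be the correlation of brain-lesion incorporation with brain-lesion response, and λ the correlation of extracranial with brain-lesion incorporation. If the extracranial value informs response only through the brain value, the observable correlation is ρ × λ. Simulated power at n = 6 (200,000 bivariate normal samples):

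| λ | ρ = 0.8 | ρ = 0.6 |
|---|---|---|
| 1 | 56% | 25% |
| 0.7 | 22% | 13% |
| 0.5 | 12% | 8% |
| 0.3 | 7% | 6% |
| 0 | 5% | 5% |

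3. **Binary response, n = 6.** The smallest two-sided exact rank-sum p with k responders is 2 / C(6, k): 2/20 = 0.10 for k = 3, 2/15 = 0.13 for k = 2, and 2/6 = 0.33 for k = 1. By symmetry k = 4 and 5 match k = 2 and 1. No split reaches 0.05.

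4. **Number of biopsies.** The calendar footnote limits biopsy to patients with an easily accessible tumour, and no accessibility rate is given. If 30% of patients qualify (assumption), 6 × 0.3 = 1.8 biopsies are expected, and the chance of none is 0.7⁶ = 0.12. At 50% (assumption), 3 are expected.

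**The case against.** Much can be said for the plan. Objective 1.3.1 openly says the biopsies are extracranial and calls the marker exploratory. Section 9.2.1 reports that tumour incorporation rose linearly with plasma IUdR under continuous infusion, so an extracranial value could act as a patient-level marker of drug exposure. The synopsis and 13.4.3 are already descriptive, and 2.6.2 already doubts the survival analysis. No decision rule uses the correlation.

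These points limit the size of the concern but do not remove it. Exploratory status excuses imprecision; it does not excuse an unstated surrogate assumption. The doubt about survival analysis is put down to mixed tumour types and extent of disease, not to the lesion mismatch, and the response analysis carries no such caution.

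A reader might go further than the documents allow in four ways:

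- **That no biopsied lesion can ever lie in the field.** The 3D-CRT field flashes beyond the skin (5.1.4.3), so a scalp or skull deposit might. Its response would still not be assessed under the plan.
- **That the correlation is meaningless in principle.** It could carry information if extracranial incorporation tracks incorporation in brain metastases. The fault is that this is neither stated nor tested.
- **That Day 8 is unjustified.** Section 2.6.2 gives two reasons. Obtaining measurable incorporation is unaffected. Avoiding a radiation effect has little force outside the WBRT field, but it matters where a site receives the palliative radiation that 5.3 allows.
- **That a tumour-to-granulocyte ratio would answer the preclinical question.** The two-fold differences in 2.4.2.2 and 9.2.1 compare IPdR with IUdR within each tissue, and this trial has no IUdR arm. Granulocyte incorporation was at most 2% in the animal studies. If human values are similar, the denominator is small and the ratio unstable.

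**Conclusion.** The concern holds in limited form. As written, regressing intracranial response on extracranial incorporation cannot support the radiosensitization label, because it rests on an unstated and untested surrogate assumption. The regression, categorical-response and Cox wording in 2.6 and 2.6.2 also conflicts with the descriptive plan in 13.4.3 and the synopsis. This part rests on the text alone. The power figures and biopsy counts depend on the assumptions shown, and the conclusion does not need them.

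The impact is confined to one exploratory objective in at most six patients. A reader might infer that dose selection is compromised, but it is not: the RP2D follows DLT counts (5.1.2, 5.1.3, 13.1), and section 2.5 leaves efficacy to future studies.

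**What to change.** In 1.3.1, 2.6 and 2.6.2:

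- Replace the RECIST regression and the Cox model with an individual listing of Day 8 extracranial tumour %IUdR-DNA beside the same patient's Day 8 granulocyte %IUdR-DNA. Section 9.2.2 already plans both measurements by HPLC.
- Flag any biopsied site that has received palliative radiation. This is a reporting flag, not a new rule for choosing the site.
- Drop the description of the measurement as a biomarker of radiosensitization. State that the values describe systemic delivery and extracranial tumour incorporation only.
- State that any side-by-side display with intracranial response is hypothesis-generating and rests on an untested surrogate assumption.
- If a tumour-to-granulocyte ratio is shown, keep it descriptive and say that it does not address the IPdR-versus-IUdR comparison.

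This brings the three sections into line with the synopsis and 13.4.3. It needs no new sample or visit, only revised wording and one flag in the listing. The real cost is that the sponsor gives up a stated exploratory biomarker claim.
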